### 7.2.2 Visit 2 (non-infusion)

As with the screening visit, the subject will be told to avoid alcohol, over the counter cold prep and NSAIDs, and strenuous exercise for 24 hours, and to eat a small meal 2-3 hours prior to coming to the laboratory. They will also be asked to refrain from items containing caffeine 12 hours prior to this visit. Women of childbearing potential (pre-menopausal) will take a urine pregnancy test to ensure they are not pregnant.

The subject will then lay supine as a Dual-Energy X-ray Absorptiometry (DEXA) scan is performed to determine fat free mass. Then the subject will then lay on an exam bed for placement of EKG pads as well as NIRS devices (one on the forearm, one on the forehead, and two on the leg) and measurement of vital signs.

The subject will then be assisted onto the recumbent bike. The Subject will be asked to squeeze a handgrip device as hard as they can with their hand. The maximum force they can exert (highest of 2 to 3 efforts) will be used to determine how hard they will squeeze this device later in the study (40% of this maximum value). A silicone face mask will be placed over the subject's nose and mouth to monitor their oxygen consumption and breathing frequency, and blood pressure devices will be placed over their arm (SunTech Tango) and finger (Finometer). After all instrumentation is in place, baseline measurements of heart rate, cardiac output, oxygen consumption, blood pressure, and NIRS will begin.

All measurements (HR, BP, cardiac output, oxygen consumption and NIRS) continue to be collected throughout the exercise protocol (some continuously, others intermittently). Once these measurements have stabilized, the subject will be asked to squeeze the handgrip device (constant tension) at 40% of the force they developed during the maximum grip testing for 1-2 minutes. Once all measurements have returned to baseline, the subjects will then begin the cycling exercise protocol, (see figure above). Subjects will be asked to pedal for 2 minutes at a very light intensity, followed immediately by 5 minutes at a light intensity, and 5 minutes of cycling at a moderate intensity. Finally, the subject will continue cycling at the same moderate intensity for 1-2 minutes while simultaneously squeezing a handgrip device at 40% of their maximal effort. The subject will then rest for 45 mins, after which they will repeat the exercise protocol. Immediately following the second exercise bout, cuffs will be placed on the upper arm and on the upper thigh of the limbs with the NIRS probes attached. The cuffs will then be inflated to ~250 mmHg until the limbs have been completely deoxygenated (~5 minutes as determined by NIRS).

At least three lactate measurements will be collected during each trial (6 total); one during rest, one after 4 mins of light intensity exercise, and one after 4 mins of moderate intensity exercise.

After the recovery period, most instrumentation will be removed (except for the blood pressure cuffs and EKG). The subject will then sit up slowly as we monitor their BP and HR, and offer them juice and crackers. Once the subject's BP and HR have returned to baseline levels, we will remove the remaining monitoring equipment and the subject may leave.

### 7.2.3 Visit 3 (Infusion)

[figure not shown]
The order of infusion will be randomized and "blinded" such that neither the subject nor the investigators will know what the infusion order is (only the nurses will know the order, for safety reasons).

As with the screening visit, the subject will be told to avoid alcohol, over the counter cold prep and NSAIDs, and strenuous exercise for 24 hours, and to eat a small meal 2-3 hours prior to coming to the laboratory. They will also be asked to refrain from items containing caffeine 12 hours prior to this visit. Women of childbearing potential (pre-menopausal) will take a urine pregnancy test to ensure they are not pregnant.

Then the subject will then lay on an exam bed for placement of EKG pads as well as NIRS devices (one on the forearm, one on the forehead, and two on the leg) and measurement of vital signs. A nurse will then insert a catheter into a vein of the subject's arm (visit 3 only). This catheter will enable us to infuse the drug (Esmolol or saline).

The subject will then be assisted onto the recumbent bike. The subject will be asked to squeeze a handgrip device as hard as they can with their hand. The maximum force they can exert (highest of 2 to 3 efforts) will be used to determine how hard they will squeeze this device later in the study (40% of this maximum value). A silicone face mask will be placed over the subject's nose and mouth to monitor their oxygen consumption and breathing frequency, and blood pressure devices will be placed over their arm (SunTech Tango) and finger (Finometer). After all instrumentation is in place, baseline measurements of heart rate, cardiac output, oxygen consumption, blood pressure, and NIRS will begin. After all instrumentation is in place baseline measurements of heart rate, cardiac output, oxygen consumption, blood pressure, and NIRS will begin.

A CRC clinician will join the research team immediately before it is time to start the infusion. The CRC clinician will be able to review the EKG results at that time if there are any concerns. The subject will then receive an infusion of Esmolol or saline. The Esmolol loading dose will be 0.5 mg/kg fat free mass/min administered over the first 3 minutes (loading dose), followed by a maintenance dose of 0.25 mg/kg fat free mass/min for the remainder of the protocol (maximum of 60 minutes).

All measurements (HR, BP, cardiac output, oxygen consumption and NIRS) will be continue to be collected throughout the exercise protocol (some continuously, others intermittently). Once these measurements have stabilized (i.e., approximately 10 minutes into the maintenance infusion), the subject will be asked to squeeze the handgrip device (constant tension) at 40% of the force they developed during the maximum grip testing for 1-2 minutes. Once all measurements have returned to baseline, the subjects will then begin the cycling exercise protocol. Subjects will be asked to pedal for 2 minutes at a very light intensity, followed immediately by 5 minutes at a light intensity, and 5 minutes of cycling at a moderate intensity. Finally, the subject will continue cycling at the same moderate intensity for 1 to 2 minutes while simultaneously squeezing a handgrip device at 40% of their maximal effort. The subject will then rest for 45 mins, after which they will repeat the exercise protocol. Immediately following the second exercise bout, cuffs will be placed on the upper arm and on the upper thigh of the limbs with the NIRS probes attached. The cuffs will then be inflated to ~250 mmHg until the limbs have been completely deoxygenated (~5 minutes as determined by NIRS).

After the recovery period, most instrumentation will be removed (except for the blood pressure cuffs and EKG). The subject will then sit up slowly as we monitor their BP and HR, and offer them juice and crackers. Once the subject's BP and HR have returned to baseline levels, we will remove the remaining monitoring equipment and the subject may leave. There is no need to send subjects home with a heart rate monitor after the study because the effects of Esmolol are very short (9-minute half-life).

Listed below are all the parameters that will be measured. The risks of each procedure are listed in Section 11.0.

1. **Oxygen consumption (VO2)**: Pulmonary oxygen consumption will be measured using a COSMED Quark breath-by-breath system. A silicone mask will be placed over the subject's nose and mouth to measure breather frequency and volume in addition to the expired gas content.
2. **Cardiac Output and Heart Rate**: Cardiac output and heart rate will be measured non-invasively using a PhysioFlow Enduro device. 6 EKG pads will be placed on the subject (2 on the neck, 2 on the chest, and 2 on the back). This device will determine heart rate using EKG and will use bioimpedance to estimate cardiac output throughout the experiment.
3. **Blood pressure**: Blood pressure and heart rate will be measured non-invasively via an automatic sphygmomanometer (SunTech Tango) and with a photoplethysmographic device (Finometer, FMS, Netherlands). To optimize the accuracy of beat-by-beat data collected by the Finometer, care will be taken to stabilize the device on the hand at heart level, and the device will be turned off between protocols to prevent finger edema, which may interfere with the ability to measure finger blood pressure. Baseline BP will be measured by the SunTech Tango and the Finometer will be adjusted to match that pressure to provide an accurate baseline pressure reading. The SunTech Tango device will not be used during the handgrip exercises because it cannot measure blood pressure under those conditions.
4. **Venous catheter**: An IV will be placed in a peripheral vein to infuse Esmolol and saline, and to withdraw blood for CBC (complete blood count) and CMP (Chem-7). The total volume of blood obtained will not exceed 50 ml. Blood will be sent to HMC Clinical Laboratory for processing.
5. **Skinfold thickness**: Doppler ultrasound will be used to measure the fat thickness at the sites of the NIRS sensors (forearm and calf).
6. **Physical activity questionnaire**: Healthy subjects will complete a physical activity history questionnaire, which is a pen and paper assessment of their estimated amount of leisure time physical activity

7. **Near infrared spectroscopy (NIRS):** We will place a wireless portable near infrared spectroscopy (NIRS) device on the forearm (non-handgrip arm), as well as on the forehead, the vastus lateralis (thigh) and the gastrocnemius (calf) muscle of one leg. These devices are essentially small plastic boxes that measure skeletal muscle oxygenation noninvasively. The system measures the hemoglobin saturation of the investigated tissue, called the 'tissue saturation index' (TSI). In addition to TSI, the system also measures oxygenation changes in terms of oxy-hemoglobin, deoxy-hemoglobin, and total hemoglobin, which is an indication of the blood volume in the tissue. At the end of study visits 2 & 3, a cuff will be placed on the upper arm and upper thigh of the limbs with NIRS attached. The cuff will be inflated to a suprasystolic pressure (~250 mmHg) to occlude blood flow to fully deoxygenate the limb. This allows for calibration of the NIRS data.
8. **Isometric handgrip exercise:** Subjects will perform a maximal voluntary handgrip using a handgrip dynamometer (highest of 2 to 3 maximum efforts). A percent maximum is calculated and set on a visual display so the subject grips at the appropriate intensity. Subjects will be asked to grip at 40% of their maximum and to maintain that grip for 90 seconds.
9. **DEXA:** Subjects will lay supine on a flat, open x-ray table and will be asked to remain very still during the scan. This will provide us with the subject's fat free mass, which will be used to determine esmolol dosing.
10. **Blood Lactate:** Before each sample is collected, the finger will be cleaned with an alcohol wipe and allowed time to dry. The blood sampling procedure will involve a single-use fingerstick device, on the 3rd and 4th fingers of the hand. The first drop will be wiped with gauze and the second drop will be collected on the test strip of the lactate analyzer.

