### 1.3 Secondary Study Endpoints

Secondary outcome variables will include the effect of concurrent sympathetic stimulation via isometric handgrip exercise on active thigh and inactive forearm muscle  $\Delta\% \Delta SmO_2$ . We will also include measurements of blood pressure, heart rate, cardiac output, and  $VO_2$ .

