## 7.2 Study Procedures

### 7.2.1 Visit 1 (screening visit)

When research staff schedules the subject (over the phone), the subject will be told to avoid alcohol, over-the-counter cold prep and NSAIDs, and strenuous exercise for 24 hours, and to eat a small meal 2-3 hours prior to coming to the laboratory. They will also be asked to refrain from items containing caffeine 12 hours prior to this visit. All participants will review their medications, including beta-blockers, with one of the research nurses. This information will be shared with the CRC clinician who will then recommend which medications can be taken prior to the patient's scheduled second and third study visit, and which ones should be withheld until after each study visit.

During the first visit, informed consent will be obtained. Women of childbearing potential (pre-menopausal) will take a urine pregnancy test to ensure they are not pregnant. This will be done at all 3 visits before conducting any of the study measurements. The subject will then complete a medical history questionnaire (all subjects) and a physical activity history questionnaire. The subject will also have their height and weight (without shoes) and waist circumference measured. The subject will then undergo a physical exam and a resting EKG (conducted by medical personnel). A venous blood draw will then be performed by a CRC nurse and sent for analysis (CBC and CMP; 7.5 ml total). Lab values will be verified/signed off by a CRC clinician before infusion begins, and will be obtained no more than 6 weeks prior to the infusion. During this first study visit, all subjects will also be asked to squeeze a handgrip device as hard as they can 3 times, with approximately 1 min recovery between each. After a short recovery, the subject will then be asked to squeeze the handgrip device for approximately 1 minute at 40% of their maximum effort. Immediately after, we will ask the subject how they tolerated the 40% grip task (rating of perceived effort scale). This procedure will familiarize the subject with the handgrip before they are asked to perform these tasks (for longer durations) during visits 2 and 3. Analysis of the blood

tests, EKG and medical history/exam results, and the subject's tolerance to the handgrip will collectively determine the final eligibility of the participant.

(Figure from Iannetta et al., 2020)

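### Does a 90-second handgrip in one place and a 1-to-2-minute grip in others leave the esmolol and saline bouts with unequal stimuli?

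*Combined protocol and SAP*

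**What the plan says.** Section 1.3 lists first among the secondary outcomes "the effect of concurrent sympathetic stimulation via isometric handgrip exercise on active thigh and inactive forearm muscle", expressed as the saline-versus-esmolol difference in the change in muscle oxygenation.

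The length of the grip appears in four places:

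- **Section 7.2.1 (Visit 1).** The practice task is to "squeeze the handgrip device for approximately 1 minute at 40% of their maximum effort". It is meant to familiarise the woman "before they are asked to perform these tasks (for longer durations) during visits 2 and 3".
- **Section 7.2.2 (Visit 2).** The resting grip is held "at 40% of the force they developed during the maximum grip testing for 1-2 minutes". Later, "the subject will continue cycling at the same moderate intensity for 1-2 minutes while simultaneously squeezing a handgrip device".
- **Section 7.2.3 (Visit 3, infusion).** The resting grip has the same range, and during exercise "the subject will continue cycling at the same moderate intensity for 1 to 2 minutes while simultaneously squeezing a handgrip device". The sequence is repeated after 45 minutes of rest.
- **Section 7.2.3, item 8 (measurement list).** "Subjects will be asked to grip at 40% of their maximum and to maintain that grip for 90 seconds".

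Section 8.3 says that changes are computed for each patient before analysis and that the crossover is handled by repeated measures ANOVA. It gives no reading window for NIRS during the grip and no rule for a grip that ends early.

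**The concern.** The outcome is a difference of differences: each woman's response to the grip under esmolol minus her response under saline, compared between age groups. It is interpretable only if the stimulus is the same in both of her bouts. If the pressor and sympathetic effects of a sustained grip build with time, a reading at 60 seconds is not the same measurement as one at 120 seconds.

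Staff who followed only the visit narrative could run the two infusion bouts at different lengths without recording a deviation. If the mismatch went one way with treatment, and differently in older and younger women, it would look like an effect of age or drug on sympatholysis. Older women stopping sooner, or stopping sooner in the second bout, is an obvious route. With no stated reading window, nothing in the analysis text would visibly correct for this.

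**Working it through.** **1. The plan's own figure.** No sample size or relevant difference is stated for the handgrip outcome. The only figure in Section 8.2 is 11 per group for the primary outcome (difference 5.8, SD 4.78, two-sided 0.05, power 80%):

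n = 2 × (1.96 + 0.8416)² × 4.78² / 5.8² = 2 × 7.849 × 22.848 / 33.64 = 10.66, rounded up to 11.

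It reproduces under the normal approximation. With the noncentral t, power is 77.2% at 11 and 84.3% at the 13 completers planned. The grip length does not enter this calculation, because the primary outcome is the response to moderate cycling.

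**2. Permitted durations and bout ratios.**

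| Reading of the text | Bout lengths | Ratio |
|---|---|---|
| Range alone, extremes | 120 s and 60 s | 120/60 = 2.0 |
| One bout at 90 s, other at the lower end | 90 s and 60 s | 90/60 = 1.5 |
| One bout at 90 s, other at the upper end | 120 s and 90 s | 120/90 = 1.33 |
| Item 8 in every bout | 90 s and 90 s | 90/90 = 1.0 |

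**3. Can all statements be met at once?** Three conditions apply to Visits 2 and 3: longer than about 60 s (Section 7.2.1), between 60 and 120 s (visit procedures), and equal to 90 s (item 8). A 90 s grip meets all three. The 2.0 in the first row needs a 60 s study grip, which the Visit 1 sentence argues against, so the ceiling under the visit sections read together is slightly below 2. The two-fold figure comes from the range alone, not from any clash between the range and item 8.

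**4. What it would take to bias the age comparison.** For each woman let d be the grip time under esmolol minus the grip time under saline, in minutes, and let b be the change in the NIRS response per minute of grip. The error in her esmolol-minus-saline value is b × d. The error in the age contrast is

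mean(b × d) in older women − mean(b × d) in younger women.

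- With 90 s in every bout, d = 0 and the error is zero.
- If lengths vary for reasons unrelated to treatment, d averages zero in both groups. The result is added noise, not a false effect.
- A false effect needs d to lean one way with treatment and b × d to differ by age group.

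The documents give no value for b. If b is assumed to be 2 to 4 points per minute, a mismatch of 0.5 to 1.0 minute gives 0.5 × 2 = 1 to 1.0 × 4 = 4 points. That is the error for one mismatched woman, not for a group mean. It should not be set against 5.8 points, which the plan names for the primary outcome.

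**5. Would a reading window tied to each woman's shortest grip help?** A window of, say, the last 15 s before her shortest completed grip matches her two bouts. A woman who holds 90 s twice is then read at 75 to 90 s, and one who stops at 60 s in either bout is read at 45 to 60 s. If older women stop sooner, the age comparison is still made at different elapsed times. That remedy would not remove the harm it is meant to address.

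**The case for a change.** The best case for a change is that nothing says the measurement list overrides the visit procedures. Staff work from the visit procedures, and repeating the protocol repeats a range, not a fixed time. A fixed target also does not deal with grips that end early. Tolerance is screened only with a grip of about 1 minute at Visit 1, Section 3.3.1 stops a procedure that is not tolerated, and Section 8.3 is silent on shortened grips. Age is not randomised, the randomisation is not described as stratified by age group, and with 13 women per group the treatment order may be unbalanced within a group. The correction would cost a few words.

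Part of this stands. The visit text alone does allow unequal bouts, and the reading window is unstated.

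The rest carries less weight. Early stopping would happen under a fixed 90 s as well, so it does not follow from the two wordings, and tolerance of the 40% grip does count towards final eligibility (Section 7.2.1). Both infusion bouts take place in one visit, at the same percentage of a maximum measured at its start, and under one instruction to repeat the protocol, which points to matched bouts without stating it. Drift in grip length driven by a visibly lower heart rate is conjecture: no section ties the end of a grip to heart rate, and Section 7.4 keeps data collectors blinded, with only the CRC nurse knowing the treatment.

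**Conclusion.** No change to the plan follows. The measurement list gives a fixed value and the visit narrative gives a range that contains it. Carrying out the whole protocol as written gives 90 s in each bout and a ratio of 1.0. The wording is loose and could be tidied whenever the protocol is next amended, but no result depends on it.

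The unstated reading window is ordinary missing detail. An analyst computing a paired difference would read both bouts at the same elapsed time and note any grip that fell short.

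The reach is limited to one secondary outcome in a study that Section 8.3 describes as small and exploratory. The primary outcome and the 11 per group are unaffected. The size and direction of any bias cannot be derived from the documents.

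This conclusion rests on three assumptions: that item 8 is the operative instruction, since it is the only exact value given; that NIRS is among the measurements Sections 7.2.2 and 7.2.3 describe as continuous, which they do not say outright; and that the protocol diagrams, which could not be read for this check, do not show a different grip time.

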### 7.3 Duration of Participation

The first visit could take up to 3 hours. Visit 2 will take up to 3.5 hours. Visit 3 will take up to 4.5 hours.

### 7.4 Test Article(s) (Study Drug(s) and/or Study Device(s))

Esmolol hydrochloride will be handled following the Institution's Standard Operating Procedures for Clinical Research Section III, PM 306. Esmolol will be tracked using an accountability record, and dispensed by a physician, pharmacist, PA, or CRNP. The receipt, storage, dispensing and return/destruction will follow the Institution's Standard Operating Procedures for Clinical Research.

- **Description**

Esmolol hydrochloride (2500 mg in 250 ml normal saline) will be purchased from McKesson in pre-mixed bags. The placebo will be a 250 ml, 500 ml, or 1000 ml bag of normal saline.

- **Treatment Regimen**

The route of administration of Esmolol in our study is the same as in clinical care (IV pump). The loading dose will be 0.5 mg/kg fat free mass/min administered over the first 3 minutes, followed by a maintenance dose of 0.25 mg/kg fat free mass/min for the remainder of the protocol (maximum of 60 minutes).

- **Method for Assigning Subject to Treatment Groups**

This study uses a crossover design so all subjects will complete both treatments in random order. Subjects will be randomized to one of two treatment sequences using an equal allocation ratio of 1:1. The two treatment sequences to which subjects will be randomized are 1) Esmolol infusion first and saline infusion second and 2) saline infusion first and Esmolol infusion second. The CRC nurses will generate the randomization that will use variable size, random permuted blocks with block size 2 and 4. CRC staff will maintain the randomization list until data collection has been completed to keep the research staff blinded.

- **Subject Compliance Monitoring**

Not applicable.

- **Blinding of the Test Article**

This study is single blind because the subjects, data collectors, and data analysts will not be aware of the treatment. For safety reasons, the CRC nurse will not be blinded. Additionally, once the Esmolol/saline infusion pump is programmed by the research nurse, an opaque bag will be placed over the fluid bag so that the participant and all investigators in the room remain blinded to the treatment order.

- **Receiving, Storage, Dispensing and Return**

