### 1.2 Primary Study Endpoints

The primary outcome variable is the difference in the change in skeletal muscle oxygenation (% $\Delta SmO_2$ ) in the active leg muscle from baseline during recumbent cycling exercise between saline and esmolol ( $\Delta\% \Delta SmO_2$ ). We predict that older women will have a greater  $\Delta\% \Delta SmO_2$  than premenopausal women during esmolol infusion.

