## 7.0 Study Design and Procedures

## 7.1 Study Design

**Design:** single blind, randomized, placebo-controlled, crossover (each person receives both treatments)

**Subjects:** young and older women (2 groups, n=13 completed subjects each)

**Independent variable:**  $\beta_1$  selective blockade with Esmolol vs. saline

[figure not shown]
**Dependent variables:** heart rate, cardiac output, arm BP, finger BP,  $\text{VO}_2$ , forearm, forehead, thigh and calf NIRS

**There will be one screening visit and two study visits (one non-infusion and one infusion).** The procedures for each visit are outlined in the diagram below:

[figure not shown]

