### **8.2 Sample size determination**

$\Delta\Delta SmO_2$  (difference between  $\% \Delta SmO_2$  during saline and esmolol trials) in response to moderate-intensity cycling exercise is our primary outcome. We do not have any pilot data pertaining to Esmolol infusion and exercise in postmenopausal women. However, using data from our recent publication, older adults ( $65.0 \pm 2.6$  years,  $n=3$ ) displayed a greater  $\Delta\Delta SmO_2$  compared to their young ( $25.4 \pm 1.9$  years,  $n=5$ ) counterparts ( $22.0 \pm 4.0$  % vs  $16.2$  %).

$\pm 4.0\%{^{20}}$ . Considering this prior data, we will consider the difference between the pre-to-post Esmolol change and the pre-to-post placebo change (i.e., delta delta) of 5.8% to be clinically relevant. Furthermore, we assume the variability (i.e., standard deviation) will be 4.78%, the standard deviation seen from this previous data. We also assume there will be no carryover effect. Given these assumptions, a sample size of 11 subjects per group will provide 80% power to detect a difference in the change in  $\% \Delta \text{SmO}_2$  between Esmolol and placebo, assuming a standard deviation of 4.78%, using a two-sided test having a significance level of 0.05. To account for differences in subject population and exercise protocol between that study and this protocol, we plan to complete data collection on 13 subjects per group to ensure sufficient power. However, we expect a small number of individuals may not complete the study. Therefore, we plan to enroll up to 20 subjects per group for a total of no more than 40 subjects so that 13 subjects per group may complete the study.

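### The plan names no stratification of infusion order by age group, so a chance order imbalance can enter the primary age contrast; separate lists plus a sequence term would close this cheaply

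*Combined protocol and SAP*

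**What the plan says.** Section 7.4 gives the allocation method in some detail: "Subjects will be randomized to one of two treatment sequences using an equal allocation ratio of 1:1". The sequences are esmolol then saline, and saline then esmolol. On the method it says: "The CRC nurses will generate the randomization that will use variable size, random permuted blocks with block size 2 and 4". On custody it says: "CRC staff will maintain the randomization list until data collection has been completed to keep the research staff blinded". The list is in the singular. Neither this section nor any other names a stratification factor.

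The comparison of interest is between age groups. Section 7.1 describes "young and older women (2 groups, n=13 completed subjects each"), and Section 1.2 states the direction: "We predict that older women will have a greater" difference than premenopausal women.

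Section 7.2.3 places both infusion bouts in Visit 3, the second after a 45-minute rest. Section 8.2 assumes no carryover and does not mention an effect of bout order. Section 8.3 plans a repeated measures ANOVA that is meant to account for the crossover, and an ANOVA between groups on each woman's change. It does not list the model terms.

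**The concern.** Permuted blocks on a common list balance the two orders over all 26 women. The primary contrast needs something else: the same esmolol-first share within each age group. On a common list a block of 2 or 4 can hold both young and older women, so the block balances the total and leaves the split within each group to chance.

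This matters if the second bout differs from the first for reasons unrelated to the drug, such as fatigue or warm-up. A woman's esmolol-minus-saline difference then carries that shift with a sign set by her order. If the age groups have different esmolol-first shares, the signs do not cancel and part of the shift is read as an age effect. With 13 women per group, the gap in share can be large in the one trial that is run.

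**Working it through.** **Inputs.** From Section 8.2: target difference 5.8, SD 4.78, two-sided 0.05, 80% power, 13 completers per group, at most 20 enrolled per group. From Section 7.4: 1:1, blocks of 2 and 4. Assumed, because the documents give no figure: a bout-order shift π (second bout minus first) of 0 to 4 percentage points, common to both age groups, and age groups arriving in random order.

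**The plan's own figure.** n = 2 × (1.960 + 0.842)² × 4.78² / 5.8² = 10.7, so 11 per group, as stated. A t-based calculation gives 77% power at 11 and 84% at 13, so the planned 13 is adequate when there is no order effect. The standard error of the age contrast is 4.78 × √(2/13) = 1.87.

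**How the shift enters.** An esmolol-first woman's difference is τ − π and a saline-first woman's is τ + π. With esmolol-first share p, a group mean is τ + π(1 − 2p). Therefore

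older − young = true difference + 2π(p_young − p_older).

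**How large the gap in share becomes** (simulated allocations, 13 completers per group):

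| Scheme | Gap ≥ 3 women | Gap ≥ 5 women |
|---|---|---|
| One list, mixed arrival | 41–42% | 11% |
| One list, 40 randomised, random 13 per group complete | 34% | 8% |
| One list, one age group enrolled wholly first | 0% | 0% |
| Two lists, 13 allocated in each | 0% (never above 1) | 0% |
| Two lists, 20 randomised in each, random 13 complete | 11% | 0.3% |

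**Error in the realised contrast**, 2π × gap/13:

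| Gap | π = 2 | π = 4 |
|---|---|---|
| 1 | 0.31 | 0.62 |
| 3 | 0.92 (16% of 5.8) | 1.85 (32%) |
| 5 | 1.54 (27%) | 3.08 (53%) |

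**Spread over repeated trials.** The SD of the gap in share is 0.20 with one list and 0.054 with two. At π = 2 the SD of the estimate is √(1.87² + (4 × 0.20)²) = 2.04 with one list and √(1.87² + (4 × 0.054)²) = 1.89 with two. At π = 4 the figures are 2.46 and 1.92.

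**Power and type I error, averaged over allocations** (simulated; these figures move by a point or two between runs):

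| Design and model | Power, π = 2 | Power, π = 4 | Type I error, π = 2 / 4 |
|---|---|---|---|
| One list, no sequence term | 78% | 62% | 5% / 5% |
| Two lists, no sequence term | 79% | 64% | 3% / 1% |
| One list, sequence term | 82% | 83% | 5% / 5% |
| Two lists, sequence term | 84% | 84% | 5% / 5% |

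**Conditional on the split drawn, no sequence term.** At a gap of 3 and π = 2, type I error stays at about 5%, but power is 63% or 91% depending on direction. At a gap of 5 and π = 2, type I error is about 10% and power is 51% or 95%. With the term, type I error at a gap of 5 returns to about 5% and power is about 77%.

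**Price of imbalance once the term is fitted.** The variance factor is 1/(1 − d²), where d is the gap in share: 1.06 at 3/13 and 1.17 at 5/13.

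**The case against.** A reader might infer that the primary comparison is biased or that its error rate is inflated. The documents do not support that. Order is randomised, so the expected gap is zero, average bias is zero and overall type I error stays near 5%. The order shift also sits within each group's spread, so the unadjusted test already widens its standard error.

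A reader might also take it as stated that the list is unstratified. It is not stated. This is read from the absence of a stratification factor and from a singular noun, and the authors could settle it in one sentence.

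Three further objections have force. First, stratification alone gains only a point or two of power and makes the unadjusted test conservative; most of the loss comes from leaving order out of the model. Section 8.3 does not rule out a period or sequence term, and its repeated measures ANOVA may be meant to include one. Second, the size of the shift is assumed. The endpoint is a change from baseline, so drift in the resting level would drop out if each bout has its own baseline. Visit 2 repeats the exercise without infusion and would measure the shift directly, although Section 8.3 makes no commitment to use it. Third, if one age group were recruited wholly before the other, blocking alone would keep the gap at 2 or less. The recruitment sections plan no such order.

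What stands is that nothing in the text secures balance of order within the two groups being compared. The trial's single estimate will carry whatever split it draws, and the split cannot be rebalanced afterwards.

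**Conclusion.** The point holds as a minor design improvement. As written, Section 7.4 does not provide for balance of infusion order within age group. With one list and mixed enrolment, a gap of 3 or more women occurs in about 42% of trials (about 34% if 40 are randomised and 13 per group complete). At an assumed 2-point shift, a gap of 3 moves the realised age contrast by 0.9 points, about half of its standard error of 1.87.

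The conclusion rests on four conditions: the list is in fact not stratified, the groups enrol in mixed order, a bout-order effect exists, and the primary model has no sequence or period term. If any one fails, little or nothing remains. The figures do not support a claim of systematic bias, or a claim that stratification by itself is the remedy.

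**What to change.** Make two changes together.

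1. In Section 7.4, state that sequence is allocated from two separate 1:1 lists, one for premenopausal and one for postmenopausal women, each with permuted blocks of 2 and 4. State that the next slot on the matching list is assigned at the start of Visit 3, so that women lost after Visit 1 or 2 use up no slots. If separate lists already exist, say so.
2. In Section 8.3, include infusion sequence (bout order) as a term in the primary age-group model. This brings most of the gain: power rises from about 78% to 82–83% at a 2-point shift, and from about 60–62% to 82–83% at 4 points. Separate lists add roughly 1 to 3 points more and keep the split within one woman when 13 are allocated per group. They should not be adopted without the term, because the unadjusted test would then be conservative.

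The cost is a second list, a sentence in each section and one residual degree of freedom (24 to 23). No women, visits or staff are added. The list change must be made before allocation begins; the model term should be fixed before unblinding.
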